#### 8.4.4. Analgesic Use

The analgesic use endpoint is the number and percentage of days with analgesic use at Week 4, 8, and 12.

Participant will be asked to record use of pain medication (names of medications) using a daily eDiary by participants.

The baseline number (percentage) of days with analgesic use will be determined based on records during the 7 days prior to randomization. The weekly number (percentage) of days with analgesic use are calculated based on the records during each week postdose (Week 1 = Day 1 to 7, Week 2 = Day 8 to 14...). If the number of days with non-missing data per period is not 7, the weekly percentage of days with analgesic use will be derived based on the records with non-missing data; the weekly number of days with analgesic use will be normalized to a 7-day period (ie,  $7 * \text{weekly percentage of days with analgesic use}$ ).

For the number (percentage) of days with analgesic use, the observed value and the changes from baseline will be summarized using descriptive statistics by treatment group and visit. In addition, the proportion of participants with any analgesic use during the week will be summarized as a responder endpoint.

#### 8.4.5. Work and School Absences

The work and school absence endpoint is the number of days of work/school missed due to SCD symptoms at Weeks 4, 8, and 12.

Participant will be asked at each study visit to record the number of days missed from school or work due to SCD symptoms.

For the number of days of work/school missed, the observed value and the changes from baseline will be summarized using descriptive statistics by treatment group and visit.

This document is confidential.

#### **8.4.6. EuroQol 5-Dimension 5-Level (EQ-5D-5L) Questionnaire**

The EQ-5D-5L endpoint is the EQ-5D-5L at Week 12.

The EQ-5D-5L questionnaire is a generic self-administered measure of health status, at scheduled study visits.

The first component consists of 5 questions assessing the following dimensions: mobility, self-care, usual activities, pain/discomfort, and anxiety/depression. Each dimension has 5 levels: no problem, slight problems, moderate problems, severe problems, and extreme problems. Responses to the 5 questions that define a health state will be converted to a utility score based on the country/region information.

The second component is a visual analog scale (VAS) asking participants to rate their health from 0 (worst imaginable health state) to 100 (best imaginable health state).

For the utility score/VAS score, the observed value and the changes from baseline will be summarized by treatment group and visit.

#### **8.4.7. Short Form Health Survey (SF-12v2)**

The SF-12v2 endpoint is the change from baseline in SF-12v2 at Week 12.

Short Form Health Survey (SF-12v2) is a widely used generic self-administered measure of health-related quality of life and measures 8 concepts of health: physical functioning, role limitations due to physical health problems, bodily pain, general health, vitality (energy/fatigue), social functioning, role limitations due to emotional problems, and mental health (psychological distress and psychological well-being). These 8 scales are aggregated into 2 summary measures: the physical component summary (PCS) and mental component summary (MCS) scores.

For PCS/MCS score, the observed value and the changes from baseline will be summarized by treatment group and visit.

#### **8.4.8. Patient Global Impression of Severity (PGI-S)**

The PGI-S is a single-item questionnaire that assesses impression of disease severity on a 5-point verbal rating scale. For question “Overall, how would you rate your SCD symptoms over the past 7 days”, 1 out of 5 answers (1=None, 2=Mild, 3=Moderate, 4=Severe, 5=Very severe) will be selected. Participants will complete PGI-S weekly using a study-specific eDiary.

For PGI-S numeric score, the observed value and the changes from baseline will be summarized using descriptive statistics by treatment group and visit. For PGI-S categorical result, the number (percentage) of participants with each category will be summarized by treatment group at each visit.

#### **8.4.9. Patient Global Impression of Change (PGI-C)**

The PGI-C is a single-item questionnaire that assesses perception of change in overall health status since the start of the study on a verbal rating scale. For question “Since the start of the study, how would you describe your overall health status”, 1 out of 7 answers (1=Very Much Worse; 2=Much Worse; 3=Minimally Worse; 4=No Change; 5=Minimally Improved; 6=Much Improved; 7= Very Much Improved) will be selected. Participants will complete this questionnaire at Week 12.

This document is confidential.

Participant responses will be categorized as disease deterioration (0–3 points), stable disease (4 points) or disease improvement (5–7 points) since the initial baseline visit.

For PGI-C categorical results, the number (percentage) of participants with each category will summarized by treatment group at Week 12.

This document is confidential.

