3.4.3 Early Termination Procedures

Patients who prematurely discontinue study drug for any reason should complete the safety and PRO assessments that are required at the End of Treatment Visit at the time of their discontinuation and should return to complete the Follow-up Visit 28 -3/+7 days after their final dose of study drug. In addition, for patients who discontinue ≥ 4 weeks post randomization and have specifically consented to participate in a cognitive debriefing interview, the site will notify the third-party vendor of the date of the patient's Early Termination Visit and their contact information; see Section 3.8.9.4.

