#### 5.4. Visit Windows

The following algorithms will be used to map the analysis visit for the on-treatment analysis.

Analysis Visit	Mapping Window (Study Day)
Week 1	Day 7 to Day 14
Week 4	Day 15 to Day 36
Week 8	Day 37 to Day 64
Week 12	Day 65 to (last dosing date + 4 days)

End of Treatment (EOT) analysis visit is defined as the last measurement taken that is on-treatment. For all endpoints other than TEAEs, 'on-treatment' is defined as the first dosing date through 4 days after the end of treatment visit (the last dosing date + 4 days).

Last dosing date needs to be considered for all mappings. eg, if participant comes in for Week 8 but is more than 4 days out of last dosing, then that visit will not be mapped to Week 8 for analysis as the participant is not 'on-treatment'.

If multiple measures are mapped to same analysis visit, the last set of records will be included in the analysis. In listings, data will be presented with visit collected, analysis visit mapped, and analysis flag.

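### PGI-C is summarised only at Week 12, so the form required at early discontinuation enters no specified summary when the last dose is on Day 60 or earlier

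*SAP*

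**What the plan says.** Collection. Protocol 3.4.3 says that patients who stop treatment early, whatever the cause, "should complete the safety and PRO assessments that are required at the End of Treatment Visit at the time of their discontinuation". In the Schedule of Events, the Week 12/EOT visit includes PGIC, EQ-5D-5L and SF-12v2. None of the three is scheduled at Week 1, 4 or 8. EQ-5D-5L and SF-12v2 are also collected before treatment and at Follow-up.

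Mapping. SAP 5.4 assigns data to analysis visits by study day. Week 8 is "Day 37 to Day 64" and Week 12 is "Day 65 to (last dosing date + 4 days" (inclusive). The section adds: "Last dosing date needs to be considered for all mappings". A visit more than four days after the last dose is not mapped. The same section provides a further analysis visit: "End of Treatment (EOT) analysis visit is defined as the last measurement taken that is on-treatment".

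Summaries. For PGI-C, SAP 8.4.9 states: "For PGI-C categorical results, the number (percentage) of participants with each category will summarized by treatment group at Week 12". SAP 8.4.6 states: "The EQ-5D-5L endpoint is the EQ-5D-5L at Week 12". SAP 8.4.7 states: "The SF-12v2 endpoint is the change from baseline in SF-12v2 at Week 12". For the last two instruments the SAP also plans summaries of observed values and changes by treatment group and visit. SAP 8 bases PRO analyses on the ITT and Evaluable Populations.

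**The concern.** The protocol asks early discontinuers for these forms, and the SAP then gives the PGI-C form nowhere to go. Its study day places it in Week 1, 4 or 8, or in no window, and PGI-C is tabulated at none of these. The tool that would hold it, the EOT analysis visit, is defined in SAP 5.4 and used for the SCD-SAF total score (8.4.1.1) and the biomarker responders (8.3.1), but 8.4.9 does not name it.

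Study drug may be stopped for adverse events (Protocol 3.4.2), so whether a form is left out may be related to what the patient would report. A table labelled ITT that is silent on these patients could look more favourable than the data collected, and more so in an arm with more early stopping. SAP 5.3 deals only with partial dates, so no rule for missing PRO values fills the gap.

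**Working it through.** **Inputs.** Windows and the four-day rule: SAP 5.4. Forms at early termination: Protocol 3.4.3 and the Schedule of Events. Tables planned: SAP 8.4.6, 8.4.7 and 8.4.9. Sample size: SAP 3.4, which reproduces as 40 + 48 = 88. Under 3:1 allocation the 48 split into 48 × 3/4 = 36 on 18 mg and 48 × 1/4 = 12 on placebo. The size was not set on statistical grounds, so there is no power figure to reproduce.

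**Step 1: where an early form lands.** Form day = last-dose day + lag, with lag 0 to 4 days if the form is to be on-treatment.

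| Last dose (day) | Lag 0 | Lag 4 |
|---|---|---|
| 5 | no window | Week 1 |
| 10 | Week 1 | Week 1 |
| 28 | Week 4 | Week 4 |
| 45 | Week 8 | Week 8 |
| 60 | Week 8 | Week 8 (Day 64) |
| 61 | Week 8 | Week 12 (Day 65) |
| 70 | Week 12 | Week 12 |

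Week 12 needs last dose + 4 ≥ 65, so the last dose must be on Day 61 or later. With a last dose on Day 60 or earlier, no on-treatment form can count at Week 12.

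**Step 2: which summary takes it.** PGI-C has a single stated time point, so these forms enter no specified summary. EQ-5D-5L and SF-12v2 forms miss the stated Week 12 endpoint but could appear in another by-visit row or in an EOT row. The SAP text names no such row, and the shells that would settle it are a separate document.

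**Step 3: how many forms.** The documents give no discontinuation rate. Assume that a share d, from 5% to 30%, stops by Day 60. Forms affected = N × d:

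- 18 mg: 36 × 0.05 = 1.8 to 36 × 0.30 = 10.8
- placebo, Amendment 4 and later: 12 × 0.05 = 0.6 to 12 × 0.30 = 3.6
- whole study: 88 × 0.05 = 4.4 to 88 × 0.30 = 26.4

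**Step 4: effect on percentages.** SAP 5.1 bases percentages on non-missing values. SAP 13.2.5.2 uses the analysis-set size. Let s be the share rating improved among patients with a Week 12 form and e the share among early stoppers, with every form completed.

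- Week 12, non-missing: s
- Week 12, analysis set: s(1 − d)
- EOT visit, all forms: s(1 − d) + e·d

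Assume s = 50% in both arms and e = 0. The difference in the improved share, 18 mg minus placebo, is then:

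| d, 18 mg v placebo | Week 12, non-missing | Week 12, analysis set | EOT, all forms |
|---|---|---|---|
| 10% v 10% | 0 | 45% − 45% = 0 | 0 |
| 20% v 10% | 0 | 40% − 45% = −5 points | −5 points |
| 30% v 10% | 0 | 35% − 45% = −10 points | −10 points |

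A one-arm example, with all counts assumed, shows the effect of the denominator. Of 36 patients, 8 stop by Day 60. Of the 28 others, 16 improve and 4 worsen. Of the 8, 1 improves and 6 worsen.

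| Rating | Week 12, non-missing | Week 12, analysis set | EOT, all forms |
|---|---|---|---|
| Improved | 16/28 = 57% | 16/36 = 44% | 17/36 = 47% |
| Worse | 4/28 = 14% | 4/36 = 11% | 10/36 = 28% |

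The planned table overstates improvement under one rule and slightly understates it under the other. The gap in worsening appears under both, but its size comes from the assumed 6 of 8.

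**The case against.** Several objections carry weight.

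- **Week 12 may mean the collected visit.** The schedules name a single Week 12/EOT visit, and SAP Tables 7 and 9 write Week 12 with EOT in brackets. The early form may have been meant to count. Against this, SAP 5.4 maps by study day and 8.4.1.1 lists Week 12 and EOT as separate time points. Usage is mixed, which is itself a reason to state the rule.
- **A reader might infer that all three instruments drop the early forms.** The documents do not support that for EQ-5D-5L and SF-12v2. Both are summarised by visit, the EOT definition is general, and both are collected at Follow-up, which early discontinuers are asked to attend.
- **A reader might infer that the results describe only treatment completers.** They do not. The window opens on Day 65 against a planned end at Day 85, so patients who stop from about Day 61 can be included. Listings of all PD-related data also keep early forms visible.
- **No bias of known size or direction is shown.** This stands. With equal stopping and equal outcomes the arm difference in the illustration stays at zero, and the denominator rule can reverse the sign for improvement within an arm.
- **Week 12 is a legitimate time point.** It is the protocol's own for EQ-5D-5L and SF-12v2 (4.2.3). PGI-C asks about change since the start of the study, so EOT would mix an answer given during titration with one given at Day 85. This is a good reason to keep Week 12, but not to leave the early forms out of every PGI-C table.

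**Conclusion.** The point holds for PGI-C as the SAP is written: with a last dose on Day 60 or earlier, the form required at discontinuation enters no specified summary, and the result labelled ITT covers only patients dosed to about Day 61 or later. For EQ-5D-5L and SF-12v2 it holds for the stated Week 12 endpoint only; whether early forms appear elsewhere cannot be checked without the shells.

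The size is unknown. The 5% to 30% range and every rating share above are assumptions. The effect depends on differential stopping, on how early stoppers rate themselves, and on whether the rule in SAP 5.1 or in 13.2.5.2 applies.

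Severity is minor. The primary objective is safety, none of the three instruments is in SAP Table 1, PGI-C is not in the protocol's endpoint list (4.2.3), and the SAP plans only descriptive summaries for them. Stopping for intolerance is reported separately through adverse events leading to discontinuation (SAP 7.2) and reasons for stopping treatment (SAP 6.1).

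**What to change.** 1. In SAP 8.4.9, 8.4.6 and 8.4.7, add a summary at the EOT analysis visit as SAP 5.4 already defines it, alongside Week 12. Which of the two is called the main summary is a matter of preference; both should be shown.
2. Reconcile SAP 5.1 with 13.2.5.2 and state the denominator in each of these tables.
3. Report by arm the number of early-termination forms included at EOT.
4. Show early-termination forms completed more than four days after the last dose separately, either flagged or as a supportive summary. SAP 5.4 does not treat them as on-treatment, so they should not be counted as EOT.

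The cost is a few lines of SAP text and one extra analysis visit in three sets of tables, with no new data collection. The drawback is that EOT mixes treatment durations, which is why Week 12 stays.

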## 9. Pharmacokinetic (PK) Analysis

The PK blood sampling will be done at predose and postdose of the following visits: Day 1, Weeks 1, 4, 8, 12, and Follow-up.

The PK plasma concentration data will be summarized at each assessed time point for PK Population by olinciguat dose level using the following descriptive statistics: n, number and percentage of values that are below the assay's limit of quantification (BLQ), mean, SD, coefficient of variation (CV) (calculated as  $100 \times SD / \text{mean}$ ), minimum, median and maximum.

The BLQ values will be analyzed as 0 in the table summaries. If more than 50% of values are BLQ, then only n, BLQ, n (%), minimum, median and maximum will be reported.

The following conventions will be used for the presentation of the descriptive statistics of PK plasma concentrations:

Table 11. PK Reporting Precision

Statistics	Degree of Precision
Minimum, Maximum	3 significant digits
Mean, Median	4 significant digits
SD	5 significant digits
CV (%)	1 decimal point

The actual sampling time of PK blood sample collection and the corresponding plasma concentration data will be listed.

This document is confidential.

## **10. Interim and Data Monitoring Committee Analyses**

No interim analyses were conducted for this study.

DMC analyses were planned and conducted, based on a separate DMC SAP.

This document is confidential.

## 11. Changes from Analysis Planned in Protocol

In Protocol Section 4.2.3 (patient-reported outcomes), both number and proportion of days of work/school missed due to SCD symptoms at Weeks 4, 8, 12 were included.

However, current SAP will summarize and analyze only the number (not proportion) of days of work/school missed due to SCD symptoms at Weeks 4, 8, 12. Since each week has 7 days, the calculated proportion of days of interest doesn't provide additional information.

This document is confidential.

## 13. Programming Considerations

### 13.1. General Considerations

- One SAS program can create several outputs.
- Each output will be stored in a separate file.
- Output files will be delivered in Word format (.rtf).
- Numbering of tables, figures, and listings (TFLs) will follow International Conference on Harmonization (ICH) E3 guidance.

### 13.2. Table, Listing, and Figure Format

#### 13.2.1. General

- All TFLs will be produced in landscape format, unless otherwise specified.
- All TFLs will be produced using the Courier New font, size 8.
- The data displays for all TFLs will have a minimum blank 1-inch margin on all 4 sides.
- Headers and footers for figures will be in Courier New font, size 8.
- Legends will be used for all figures with more than 1 variable, group, or item displayed.
- TFLs will be in black and white (no color), unless otherwise specified.
- Specialized text styles, such as bolding, italics, borders, shading, and superscripted and subscripted text, will not be used in the TFLs, unless otherwise specified.
- Only standard keyboard characters will be used in the TFLs. Special characters, such as non-printable control characters, printer-specific, or font-specific characters, will not be used. Hexadecimal-derived characters will be used, where possible, if they are appropriate to help display math symbols (e.g.,  $\mu$ ). Certain subscripts and superscripts (e.g.,  $\text{cm}^2$ ,  $\text{C}_{\text{max}}$ ) will be employed on a case-by-case basis.
- Mixed case will be used for all titles, footnotes, column headers, and programmer-supplied formats, as appropriate.

#### 13.2.2. Headers

- All output should have the following header at the top left of each page:

Cyclerion Therapeutics C1701-202

Draft/Final Run

- All output should have Page n of N at the top or bottom right corner of each page. TFLs are internally paginated in relation to the total length (i.e., the page number should appear sequentially as page n of N, where N is the total number of pages in the table).
- The date output was generated should appear along with the program name as a footer on each page.

This document is confidential.

### 13.2.3. **Display Titles**

- Each TFL is identified by the designation and a numeral. (i.e., [Table 14.1.1](#)). The title is centered. The analysis set is identified on the line immediately following the title. The title and table designation are single spaced. A solid line spanning the margins will separate the display titles from the column headers. There will be 1 blank line between the last title and the solid line.

Table x.y.z  
First Line of Title  
Second Line of Title if Needed  
(XX Analysis Set)

### 13.2.4. **Column Headers**

- Column headings are displayed immediately below the solid line described above in initial upper-case characters.
- Analysis set sizes will be presented for each treatment group in the column heading as (N=xx) (or in the row headings, if applicable). This is distinct from the 'n' used for the descriptive statistics representing the number of participants in the analysis set.
- The order of treatments in the tables and listings will be Placebo first in the case of placebo-controlled studies and Active comparators first in the case of active comparator trials, followed by a total column (if applicable).

### 13.2.5. **Body of the Data Display**

#### 13.2.5.1. **General Conventions**

Data in columns of a table or listing are formatted as follows:

- Alphanumeric values are left-justified;
- Whole numbers (e.g., counts) are right-justified;
- Numbers containing fractional portions are decimal aligned.

#### 13.2.5.2. **Table Conventions**

- Units will be included where available.
- If the categories of a parameter are ordered, then all categories between the maximum and minimum category are presented in the table, even if n=0 for all treatment groups in a given category that is between the minimum and maximum level for that parameter.
- If the categories are not ordered (eg, medical history, reasons for discontinuation), only those categories for which there is at least 1 participant represented in 1 or more groups are included.
- Unless otherwise specified, the estimated mean and median for a set of values are printed out to 1 more significant digit than the original values, and standard deviations are printed out to 2 more significant digits than the original values. The minimum and maximum should report the same significant digits as the original values.

This document is confidential.

- P-values are output in the format: “0.xxx”, where xxx is the value rounded to 3 decimal places. Every p-value less than 0.001 will be presented as <0.001. If the p-value are less than 0.0001, then present as <0.0001. If the p-value is returned as >0.999, then present as >0.999.
- Percentage values are printed to one decimal place, in parentheses with no spaces, one space after the count (e.g., 7 (12.8%), 13 (5.4%)). Unless otherwise noted, for all percentages, the number of participants in the analysis set for the treatment group will be the denominator. Percentages after zero counts should not be displayed and percentages equating to 100% are presented as 100%, without decimal places.
- Where a category with a subheading (such as system organ class) has to be split over more than one page, output the subheading followed by “(cont)” at the top of each subsequent page. The overall summary statistics for the subheading should only be output on the first relevant page.

#### 13.2.5.3. Listing Conventions

- Listings will be sorted for presentation in order of treatment groups as above, participant number, visit/collection day, and visit/collection time.
- Missing data are represented on participant listings as either a hyphen (“-”) with a corresponding footnote (“- = unknown or not evaluated”), or as “N/A”, with the footnote “N/A = not applicable”, whichever is appropriate.
- Dates are printed in SAS DATE9.format (“ddMMMyyyy”: 01JUL2000). Missing portions of dates are represented on participant listings as dashes (--JUL2000). Dates that are missing because they are not applicable for the participant are output as “N/A”, unless otherwise specified.
- All observed time values are to be presented using a 24-hour clock HH:MM or HH:MM:SS format (e.g., 11:26:45, or 11:26). Time will only be reported if it was measured as part of the study.
- Units will be included where available.

#### 13.2.6. Footnotes

[figure not shown]
- A solid line spanning the margins will separate the body of the data display from the footnotes.
- All footnotes will be left justified with single-line spacing immediately below the solid line underneath the data display.
- Footnotes should always begin with “Note:” if an informational footnote, or 1, 2, 3, etc. if a reference footnote. Each new footnote should start on a new line, where possible.
- Footnotes will be used sparingly and add value to the table, figure, or listing. If more than six lines of footnotes are planned, then a cover page is strongly recommended to be used to display footnotes, and only those essential to comprehension of the data will be repeated on each page.
- The last line of the footnote section will be a standard source line that indicates the name of the program used to produce the data display, date the program was run, and the listing source (i.e., ‘Program : xxx.sas Table Generation: ddmmmyyyy).

This document is confidential.

[figure not shown]
